#### 9.3 Data collection

Data will be collected using a centralized electronic case report form called **ON**-line **C**linical **O**ncology **R**esearch **E**nvironment = **Oncore**.

# 9.4 Risks and Safety

9.4.1 Adverse Event Descriptions and Grading Scales

The NCI Common Terminology Criteria for Adverse Events (CTCAE) version 4.03 will be used for the characterization and grading of adverse events.

#### 9.4.2 Time Span for Reporting Adverse Events

Reporting of AEs will begin when the participant is administered the study drug or has a study related biopsy. Events occurring through 30 days after administration of the last dose of 6MHP vaccine or ipilimumab, regardless of attribution, will be reported. AEs should be followed to resolution or stabilization. If an AE worsens and becomes an SAE, it should be reported as serious per the guidelines specified for SAE reporting.

AEs that are possibly, probably, or definitely related to any of the study drugs will be recorded until the participant completes treatment follow-up. If, during treatment follow-up, the participant receives an alternative anti-cancer treatment, participants will be off treatment follow-up and will be followed yearly for disease progression and survival.

# 9.4.3 Agent-Specific Expected Adverse Events List:

Any AE not in this list will be considered an unexpected AE.

#### Expected toxicities related to 6MHP

The list of expected AEs for the 6MHP vaccine is based on prior data from the UVA-Mel41 and Mel44 clinical trials, plus the ECOG trial E1602; from these trials, aggregated data are available from over 200 patients vaccinated with the 6MHP vaccine in an emulsion with Montanide ISA-51 adjuvant, with or without GM-CSF. These data are summarized in Table 3 and Table 4 in section 1.

# Expected toxicities related to ipilimumab

Adverse events reported for treatment of patients with the CTLA-4 antibody ipilimumab have been reported and are summarized in section 1 and Table 5 and Table 6. Interactions with the toxicities of the 6MHP vaccine are not expected, but toxicities will be tracked.

#### Adverse events expected from tumor and node biopsies.

Below is a list of expected AEs related to tumor and SIN biopsies:

- bleeding
- bruising
- pain

- infection
- lymphedema
- delayed wound healing
- scarring
- numbness

#### 9.5 Adverse Event Classifications

Adverse events (AEs) are classified into sections, specified in the CTCAE v4.03. For specific classifications pertaining to the protocol, we specify the following:

Hematologic/Metabolic- Any AE coded under one of the following CTCAE v4.03 categories should be reported under the Hematologic/Metabolic adverse event classification:

Section	AE
Blood and lymphatic	Anemia
Blood and tymphatic	Leukocytosis
	ALL EXCEPT:
	Carbon monoxide diffusing capacity decreased
	Ejection fraction decreased
Investigations	Forced expiratory volume decreased
	Vital capacity abnormal
	Weight gain
	Weight loss
	ALL EXCEPT:
	Alcohol intolerance
	Anorexia
Metabolism and nutrition	Dehydration
disorders	Glucose intolerance
	Iron overload
	Obesity
	Tumor lysis syndrome

 Table 9:
 Hematologic/Metabolic Classifications

Non-hematologic/Non-Metabolic- Any AE not reported under

hematologic/metabolic, ocular, or allergic/autoimmune, should be reported under the non-hematologic/non-metabolic adverse event classification.

Ocular – Any AE coded under one of the following CTCAE v4.03 Adverse Event Terms should be reported under the Ocular adverse event classification:

- Eye Disorders: Night blindness (nyctalopia)
- Eye Disorders: Papilledema
- Eye Disordersl: Retinopathy
- Eye Disorders: Blurred vision
- Eye Disorders: Flashing lights
- Eye Disorders: Floaters

Participants will be referred for an ophthalmologic exam if any of these ocular adverse events occur.

Allergic/Autoimmune – Only AEs coded as Immune System Disorder: Allergic reaction, autoimmune disorder, or anaphylaxis should be reported under the Allergic/Autoimmune adverse event classification. Other AEs coded under Immune System Disorder should be reported under Non-hematologic/Non-metabolic adverse event classification.

#### 9.6 Reporting Adverse Events

9.6.1 Process for Reporting AEs:

#### **Dose-limiting toxicities**

DLTs will be entered into Oncore within 5 calendar days of the study team learning of the event. DLT's that are deemed serious and unexpected will be submitted to the IRB per institutional guidelines (see below).

#### Other AEs

AEs must be recorded into the University of Virginia Cancer Center OnCore database per the following guidelines (Table 10)

	High Risk Studies Reporting requirements for AEs that occur within 30 days of the last dose of protocol specified treatment													
	Grade 1	Gra	ade 2		Grade 3									
	Expected and unexpected	Expected and unexpected Expected Unexpected			cted With hospitalization	Unexp Without hospitalization	ected With hospitalization	Expected and Unexpected						
Unrelated Unlikely	OnCore 30 days a	OnCore 30 days	OnCore 30 days	OnCore 30 days	OnCore 15 days	OnCore 30 days	OnCore 15 days	OnCore 7 days						
Possible Probable Definite	OnCore 30 daysª	OnCore 30 days	OnCore 15 days	OnCore 30 days	OnCore 15 days	OnCore (24-hrs)* 7 days								

# Table 10: AE reporting

\*Enter into OnCore database within 24 hours if unexpected and definitely related to protocol specified treatment

Hospitalization defined as an inpatient hospital stay or prolongation of a hospital stay equal to or greater than 24 hours

a Grade 1 unexpected or expected hematologic/metabolic events will be recorded in the Cancer Center Database; however, regardless of attribution, these events do not have to be reported.

#### Pregnant-Partner Outcomes

If a male has been exposed to the investigational agent prior to or around the time of conception, this will not be considered an SAE. The HITC will ask permission of the pregnant partner to be followed until term.

#### Pregnancy

If a female has been exposed to the investigational agent prior to or around the time of conception, this will not be considered an SAE. The HITC will follow the pregnancy until term.

# 9.6.2 IRB Reporting Requirements

The University of Virginia is responsible for reporting to the UVA IRB-HSR per the following guidelines (Table 11):

Table 11:	ινα	IRB-HSR	reporting
	017		reporting

Type of Event	To whom will it	Time Frame for	How reported?
	be reported:	Reporting	
Any internal event resulting in death that is deemed DEFINITELY related to (caused by) study participation (Note: An internal event is one that occurs in a subject enrolled in a UVa protocol.)	IRB-HSR	Within 24 hours	IRB Online and phone call www.irb.virginia.edu/
Internal, Serious, Unexpected adverse event.	IRB-HSR	Within 7 calendar days from the time the study team received knowledge of the event. Timeline includes submission of signed hardcopy of AE form .	IRB Online www.irb.virginia.edu/
Unanticipated Problems that are not adverse events or protocol violations This would include a Data Breach.	IRB-HSR	Within 7 calendar days from the time the study team received knowledge of the event.	Unanticipated Problem report form. http://www.virginia.edu/vprgs/irb/ HSR_docs/Forms/Reporting_Re guirements- Unanticipated_Problems.doc )
Protocol Violations ( The IRB-HSR only requires that MAJOR violation be reported, unless otherwise required by your sponsor, if applicable. ) Or Enrollment Exceptions	IRB-HSR	Within 7 calendar days from the time the study team received knowledge of the event.	Protocol Violation and Enrollment Exception Reporting Form http://www.virginia.edu/vprgs/irb/ hsr_forms.html

Data Breach	The UVa Corporate Compliance and Privacy Office and	As soon as possible and no later than 24 hours from the time the incident is identified.	UVa Corporate Compliance and Privacy Office- [contact]
	ITC: if breach involves electronic data-	As soon as possible and no later than 24 hours from the time the incident is identified.	ITC: Information Security Incident Reporting procedure, http://www.itc.virginia.edu/securit y/reporting.html
	UVa Police if breach includes such things as stolen computers.	IMMEDIATELY.	Phone- [contact]

9.6.3 Additional Reporting Requirements for the Sponsor (UVA)

# **Reporting to the FDA**

- Serious and unexpected suspected adverse reactions will be reported to the FDA no later than 15 calendar days after the sponsor determines that the requirements for an IND safety report have been met. The FDA will be notified using an FDA Form 3500a.
- Unexpected fatal or life-threatening suspected adverse reactions will be reported to the FDA no later than 7 calendar days after the Sponsor receives the initial information of the event. The FDA will be notified using an FDA Form 3500a.
- Other adverse event information will be sent to the FDA in the IND annual report.
- 9.6.4 Reporting of Participant Withdrawals/Dropouts Prior to Study Completion

Participants who withdraw consent and those dropping out of the study secondary to an AE will be reported to the UVA IRB yearly on the IRB continuation form.

# 9.7 Adverse Event Review and Monitoring

9.7.1 Capturing Adverse Events

In addition to clinic notes, adverse events will be initially captured using study-specific tools and participant toxicity diaries.

Each participant will be evaluated by a licensed clinician. The following will be performed as designated in the protocol: routine disease-directed physical exam including performance status and blood collection for clinical labs.

Participants should keep a daily diary of toxicities until FUv1. The diaries will be reviewed by a research clinician prior to the next scheduled visit. During clinic visits, participants will also be asked about subjective symptoms including headache, malaise, fatigue, dyspnea, nausea, rash, diarrhea, abdominal discomfort, peripheral nerve pain, visual changes, appetite, tremors, night sweats, and ability to concentrate. Additional toxicities will be captured from laboratory tests.

After administration of each 6MHP vaccine, participants will be observed for AEs for at least 20 minutes. Follow-up phone calls will be made per the judgment of the research clinicians with regard to individual participant need. Participants will be instructed on how to reach their provider should they have any questions and/or problems during the study.

#### 9.7.2 Review of Adverse Events by the Study Team

Individual AEs will be reviewed by the treating physician, principal investigator, and the clinical research coordinator(s) (CRC). Other staff on the research team may also review AEs.

SAEs will be reviewed about once per month by the PI and Sponsor during the UVA Melanoma Team Meeting. This meeting will occur at least 20 times in a calendar year. Those present at the meeting may include the sponsor/overall study PI, sub-investigators, protocol development staff, biostatisticians, research nurses, research coordinators, laboratory specialists, and laboratory research managers. These meetings also include the review of individual participants to assess whether they are protocol candidates, whether AEs warrant discontinuation, and whether existing protocols should be continued or closed.

#### 9.8 Recording Laboratory Values

The following laboratory values will be recorded in the UVA Cancer Center database, graded using the CTCAE v4.03 (if a grading category exists), and reported as described in Section 9.6:

- 1. Alk Phosphatase
- 2. ALT (SGPT)
- 3. ANA
- 4. AST (SGOT)
- 5. Bilirubin, total
- 6. Creatinine
- 7. Eosinophil #
- 8. Hepatitis C serology or virus measures
- 9. beta-HCG
- 10. Hgb
- 11. HĪV
- 12. HLA type
- 13. LDH
- 14. Potassium
- 15. RF
- 16. Urinalysis
- 17. WBC
- 18. Cortisol
- 19. TSH
- 20. Free T4

Any abnormal laboratory values captured which are not included in the above list, but are considered to be pertinent positive clinical signs/symptoms, and laboratory results obtained as part of routine care of patients will be recorded in the UVA Cancer Center database and reported as described in Section 9.6. If there is any doubt on the part of study personnel concerning what constitutes a pertinent positive finding, the PI and sponsor will be consulted.

# 9.9 **Dose-limiting Toxicities (DLT)**

#### 6MHP

A DLT of the 6MHP vaccine is defined as any unexpected Grade 3 or greater hematologic or non-hematologic toxicity that is definitely, probably, or possibly related to the administration of the vaccine. Small ulcerations of the skin at vaccine sites are expected. Thus, ulcerations will be considered DLTs only if the ulcers are  $\geq 2$  cm in diameter, require antibiotics or surgical debridement.

# **Ipilimumab**

A DLT of ipilimumab is defined as any toxicity that is definitely, probably, or possibly related to the administration of ipilimumab and requires permanent discontinuation of ipilimumab.

If a DLT occurs and cannot be attributed to either the 6MHP or ipilimumab, then a DLT will be attributed to both.

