# Treatment Regimen:

All patients will receive 1) the 6MHP vaccine administered in Montanide ISA-51 adjuvant (incomplete Freud's adjuvant) and 2) ipilimumab, an anti-CTLA-4 blocking antibody. Ipilimumab will be administered at 3 mg/kg IV infusion on days 1, 22, 43, and 64. Vaccines will be administered days 1, 8, 15, 43, 64 and 85. On days when both ipilimumab and vaccine are administered, the vaccine may be administered before or after ipilimumab, but preferably before. All peptide vaccines will be administered intradermally and subcutaneously. Blood and biopsy samples of a vaccine-draining node and tumor will be analyzed for immunologic changes. Details are provided in the protocol schema (Figure 1, Figure 2, Figure 3) and in the study calendar (x-page; Appendix 1).

Figure 2: Protocol Schema Cohort 2

Figure 3: Protocol Schema Cohort 3

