6.5.1 Dose Delays Due to Toxicity

- In circumstances where assessment of an AE is limited, such as by intercurrent illness, or when laboratory studies are required to assess for other causes of toxicity, the vaccine schedule may be interrupted for up to 21 days. Delay of one vaccine administration by up to 21 days will not be considered a protocol violation if due to an AE, regardless of attribution. If more than one vaccine is delayed by 21 days due to an AE, regardless of attribution, vaccine treatment should be discontinued, though the other systemic therapy may be continued.
- Dose delays for ipilimumab will follow standard clinical guidelines.

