# 8.5 Safety Monitoring

Toxicities will be monitored using CTCAE 4.03 criteria, with a focus on recording immune-related adverse events (irAE) (9). Stopping rules will be based on an expected irAE rate of 15-20%, where 10-15% had grade 3-4 irAE in one study (38) and in another 19% had grade 3, and 3.2% grade 4 irAEs (59). Significant increases over these rates are not expected but would be a reason for early discontinuation. Thus, formal safety bounds based upon the observed number of participants who experience a DLT as defined in Section 9.9 will guide decisions about early stopping due to potential safety concerns (Table 8). The definition of

DLT considers both irAEs and previously reported DLTs related to vaccine. If a stopping bound is crossed then accrual to the study will be suspended until the study PI, co-investigators and the DSMC can review the data, and determine if the study should continue, be amended or be closed to further accrual. The rate of DLTs will be monitored up to 30 days after the last vaccination. A sequential probability ratio test (SPRT) based upon a binomial test of proportions for DLTs will be used. Only the upper boundary will be used for monitoring to protect against excessive failure rates. The stopping boundary are for a SPRT contrasting a 15% versus 30% DLT rate, with nominal type I and II errors of 10% and 10%, respectively. The slope of the parallel lines for monitoring is 0.219 and the intercept for the upper bound is 2.476.

•	ie o. Otopping Oulde	
	Number of participants	Boundary
	4-6	≥4
	7-11	≥ 5
	12-15	≥6
	16-20	≥7
	21-25	≥ 8
	26-27	≥ 9

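### The DLT window in 8.5 follows the last vaccination only, and 9.9 does not say whether a first ipilimumab toxicity after the final dose counts, so the Table 8 count can omit late ipilimumab events

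*Combined protocol and SAP*

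**What the plan says.** **Schedule.** The synopsis gives four ipilimumab doses: "Ipilimumab will be administered at 3 mg/kg IV infusion on days 1, 22, 43, and 64". The sixth and last vaccine is planned for day 85.

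**Window.** Section 8.5: "The rate of DLTs will be monitored up to 30 days after the last vaccination".

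**Ipilimumab DLT (9.9).** The toxicity must be at least possibly "related to the administration of ipilimumab and requires permanent discontinuation of ipilimumab". There is no grade criterion, and nothing is said about events that arise once dosing is complete.

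**Vaccine DLT (9.9).** This is "any unexpected Grade 3 or greater hematologic or non-hematologic toxicity" at least possibly related to the vaccine, with a separate rule for ulceration.

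**Stated intent (8.5).** The definition of "DLT considers both irAEs and previously reported DLTs related to vaccine", and the rule starts from background irAE rates: "Stopping rules will be based on an expected irAE rate of 15-20" per cent.

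**Stopping one agent.** After repeated vaccine delays for an AE, 6.5.1 says "vaccine treatment should be discontinued, though the other systemic therapy may be continued". It leaves ipilimumab delays to standard clinical guidelines. Section 6.6 allows either agent to be stopped, for reasons that include participant request and investigator discretion.

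**AE reporting (9.4.2).** All AEs are reported to 30 days after the last dose of either agent, whatever the attribution.

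**The concern.** The DLT count is the only input to Table 8. An ipilimumab event that falls outside the 8.5 window, or that 9.9 does not clearly admit, can only lower the count and make a crossing less likely. Section 8.2.1 says the stopping rules are meant for toxicity beyond that of ipilimumab alone, and it names hypophysitis after ipilimumab plus other vaccines as the worry. A count that depends on which agent was given last, or on how an assessor reads one verb, serves that purpose poorly. Two assessors could also class the same late event differently.

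**Working it through.** **1. The window.** Let V be the day of last vaccination and L the day of the last ipilimumab dose. Section 8.5 closes on day V + 30, so it covers V + 30 − L days after the last ipilimumab dose. It covers a full 30 days only when V ≥ L.

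| Case | V | L | 8.5 closes | Days covered after L | 9.4.2 closes |
|---|---|---|---|---|---|
| Full planned schedule | 85 | 64 | 115 | 51 | 115 |
| Vaccine ends after vaccine 4, ipilimumab completed | 43 | 64 | 73 | 9 | 94 |
| Vaccine ends after vaccine 3 by participant request or investigator discretion (6.6), ipilimumab completed | 15 | 64 | 45 | none (closes 19 days before the dose) | 94 |

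Delayed ipilimumab has the same effect. With vaccines on schedule, a fourth dose delayed by more than 85 − 64 = 21 days falls after the last vaccination, and coverage drops below 30 days. For toxicity delays of ipilimumab, 6.5.1 sets no limit of its own.

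**2. The definition.** On the full schedule, 115 − 64 = 51 of 115 days (44%) follow the last ipilimumab dose. Read literally, a completed drug cannot need discontinuing, so an ipilimumab-only event that first arises in those days is not a DLT. Read as a severity test (serious enough that the drug would be stopped), it is.

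The vaccine limb catches some of these events, but not predictably:
- Section 9.1.2 makes anything listed in Tables 3–6 expected, and Table 5 lists hypophysitis, so the vaccine limb would not count it.
- The 4% rule in 1.6 makes grade 3 hypophysitis unexpected: 4/511 = 0.8%.
- Section 9.4.3 lists expected events by agent, and hypophysitis is not on the 6MHP list.

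The sentence in 9.9 assigning an unattributable DLT to both agents applies only once the event is already a DLT.

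**3. The plan's own bound.** Inputs from 8.5: p0 = 0.15, p1 = 0.30, α = β = 0.10.
- D = ln[p1(1 − p0) / (p0(1 − p1))] = ln(0.255/0.105) = 0.887
- slope = ln[(1 − p0)/(1 − p1)] / D = 0.2188
- intercept = ln[(1 − β)/α] / D = 2.4763

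These match the stated 0.219 and 2.476. Rounding the line up reproduces Table 8 at every n from 4 to 27 except n = 16, where the line (5.977) gives 6 and the table 7. That does not bear on this point, and I use the table as printed.

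**4. Sensitivity to an undercount.** I computed the exact probability of crossing Table 8 at any look from n = 4 to 27, adding one participant at a time and absorbing paths that reach the bound. This is the overall bound, not the within-cohort one. Let f be the share of participants with a DLT whose only qualifying event is not counted. The counted rate is then p(1 − f). **The documents give no value for f; 5%, 10% and 20% are assumptions.**

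| True rate p | f = 0 | f = 5% | f = 10% | f = 20% |
|---|---|---|---|---|
| 30% | 55.4% | 48.9% | 42.3% | 29.6% |
| 20% | 15.3% | 12.5% | 10.0% | 6.1% |

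The counted rates are 0.285, 0.27 and 0.24 in the first row, and 0.19, 0.18 and 0.16 in the second.

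**The case against.** **'Requires' may already be a severity test.** Section 6.4.2 sends ipilimumab dose changes to practice guidelines, the package insert and a management guide, and 9.10 does much the same for toxicity management. The phrase can therefore mean an event for which those sources call for permanent discontinuation, whether or not a dose remains. This is plausible and would close the 9.9 gap. It makes the problem an unresolved wording, not a proven exclusion. It does not touch the 8.5 window.

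**Few participants are involved.** Table 8 counts participants, so a late event in someone already counted changes nothing. A participant whose vaccine is stopped for a vaccine DLT is already in the count. What remains is those whose only qualifying event is late and not caught by the 6MHP definition. This stands.

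**6.5.1 rarely produces a large window gap.** It stops vaccine only after more than one vaccine is delayed by 21 days for an AE. If a delayed vaccine 4 is given on day 64, the window runs to day 94, exactly 30 days after the last planned ipilimumab dose. The day-45 case therefore rests on request or discretion under 6.6. A reader might infer that 6.5.1 alone routinely closes the window before day 64; the text does not support that.

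**Nothing is hidden.** Section 9.4.2 reports all AEs to 30 days after the last dose of either agent, and records related AEs until treatment follow-up ends (up to 24 months under 6.1). The DSMC reviews all AEs and the application of the stopping rules and meets monthly (9.12). The bounds are non-binding (8.6). A reader might infer that late irAEs go unseen, or that every late irAE drops out of Table 8. Neither follows: the weakness is in the formal count only, and late events that meet the vaccine definition still enter it.

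**Conclusion.** Both gaps are real and modest. The window gap in 8.5 does not depend on any reading of 9.9: wherever the last ipilimumab dose falls after the last vaccination, DLT monitoring ends sooner than the AE window in 9.4.2, and it may end before that dose is given. The 9.9 gap depends on the literal reading; the text does not say whether that or the severity reading applies.

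The direction is certain, since any omitted event lowers the count. The size is unknown. The crossing probabilities show what a given undercount would do to Table 8; they do not estimate the loss in this trial, and it would be wrong to read them as lost power attributable to these clauses. The days quoted are planned days, and delays move them. With AE reporting, DSMC review and a non-binding bound in place, this is a low-cost correction to the input of the only formal safety rule, not evidence that participants would be left unmonitored.

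**What to change.** - **Section 8.5:** monitor DLTs *up to 30 days after the last dose of 6MHP vaccine or ipilimumab, whichever is later*. This aligns the section with 9.4.2 and leaves day 115 unchanged on the full schedule.
- **Section 9.9, ipilimumab:** count a related toxicity that *requires permanent discontinuation of ipilimumab, or would have required it had further doses been scheduled*. The clinical criteria for discontinuation stay with the clinical team.

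**Cost.** Two clauses, with no new visit or test, because the AE data are already collected over that window. For late events someone must make and record a counterfactual judgement, which may not remove all disagreement between assessors.

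The DLT count may rise slightly, and Table 8 is not recalibrated for that. With complete counting it is crossed 4.5% of the time at a true 15% rate, 10.0% at 18% and 15.3% at 20%. At 22.2% it is crossed 22.6% of the time; that rate is 19% + 3.2% from the study in which "another 19% had grade 3, and 3.2% grade 4 irAEs", taking the grades as non-overlapping. Above about 18% the crossing rate therefore exceeds the nominal 10%. A crossing leads only to suspension of accrual for review (8.2.1), so this price is acceptable.
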